## 8.5. Stopping rules

The study will be monitored to ensure that the occurrence of a specified set of treatment related serious adverse events (TRSAEs) that occur during the treatment period does not substantially exceed an anticipated rate. The following specified TRSAEs determined to be probably or definitely related to EPAG will be considered for early stopping of the study:

- 1. Death considered to be probably or definitely related to eltrombopag
- 2. Any Grade IV toxicity excluding readily reversible metabolic or laboratory abnormalities
- 3. Grade IV thrombosis/embolism

We anticipate the rate of these specified TRSAEs within the 24-week study period to be 20% or less. Following Geller *et al.* (90), our stopping rule is determined by a Bayesian approach. The stopping boundary for an experiment is reached if the Bayesian posterior probability that the true probability of developing one or more of the specified TRSAE's exceeds this benchmark rate of 20% is at least 90%. We take our prior distribution to be a beta distribution with parameters ( $\alpha$ ,  $\beta$ ) = (1, 4). The parameters are chosen so that the mean  $\alpha / (\alpha + \beta) = 0.2$  as the expected proportion of specified TRSAE's and the sum  $\alpha + \beta = 5$  as the "worth" we place on our prior clinical opinion. This indicates that the relative weight we place on our prior opinion is 5/25=20% of the weight we will place on the results of the new study. Hence when we make decisions about stopping the study, the data from the study will dominate over the prior opinion. All participants will be included in monitoring and evaluation for safety. Table 5 summarizes the threshold numbers for stopping the study.

Number of subjects in the experiment	Stop if the number of subjects who have developed any of the specified TRSAE's reaches:
≤ 5	3
≤ 9	4
≤ 12	5
≤ 16	6
≤ 20	7
≤ 24	8

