#### Table 5: Threshold numbers for stopping the study

Number of subjects in the experiment	Stop if the number of subjects who have developed any of the specified TRSAE's reaches:	
25	9	

We investigated the performance of the above stopping rule by a simulation study. In each simulation run, we generated a study with 25 independent Bernoulli trials, each had a probability p for having TRSAE and q=1-p for not having TRSAE and compared the TRSAE outcomes with the above stopping boundary to determine whether the study was stopped. We repeated the simulation 100,000 times and computed the proportion of stopped studies (*i.e.* "number of stopped studies"/100,000) which were stopped using the above stopping rule. Table 6 summarizes the proportion of stopped studies under a number of scenarios for p:

Table 6: Predicted rates of stopping under various scenarios

Probability of TRSAE = p	0.10	0.15	0.20	0.25	0.30	0.35	0.40	0.45
Proportion of stopped studies	1.8%	7%	18.2%	35.7%	55.5%	73.2%	86.4%	94.1%
Average number of subjects	24.7	23.9	22.4	20.1	17.3	14.5	11.8	9.7
Average number TRSAEs	2.5	3.6	4.5	5	5.2	5.1	4.7	4.3

These simulation results suggest that our stopping rule has a low probability stopping a study when the proportion of TRSAE within the 24-week is below 20%, and the probability of stopping a study is high when the true proportion of TRSAE within the 24-week exceeds 20%. Therefore, we believe that our Bayesian stopping rule for TRSAE has satisfactory statistical properties.

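### The stopping probabilities in Table 6 hold only if each 24-week safety outcome is known before the next subject enters, and the Table 5 denominator is not defined for subjects still in follow-up

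*Combined protocol and SAP*

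**What the plan says.** Section 8.5 fixes the benchmark over a follow-up window: "We anticipate the rate of these specified TRSAEs within the 24-week study period to be 20% or less". The study stops when the posterior probability that the rate exceeds 20% is at least 90%, under a Beta(1, 4) prior.

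Table 5 turns this into counts. Its left column is the "Number of subjects in the experiment". Its right column reads "Stop if the number of subjects who have developed any of the specified TRSAE's reaches" a given number: 3 for up to 5 subjects, 4 up to 9, 5 up to 12, 6 up to 16, 7 up to 20, 8 up to 24, and 9 at 25. The section adds: "All participants will be included in monitoring and evaluation for safety".

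Table 6 gives the rule's performance. It comes from a simulation described this way: "In each simulation run, we generated a study with 25 independent Bernoulli trials, each had a probability p for having TRSAE". The outcomes are compared directly with the boundary. No entry dates, event dates or follow-up times are mentioned. From Table 6 the section concludes that the rule performs satisfactorily.

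Section 8.3 projects accrual over 2.5 to 3 years. It enrols 15 subjects, then 10 more if enough of the first 15 respond at 6 months.

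**The concern.** A 24-week event rate is not known for a subject in week 3. The plan does not say whether that subject is in the Table 5 denominator. The choice matters because the threshold rises with the denominator: four events among nine subjects stop the study, but four among ten do not. Adding one newly entered subject can therefore move the boundary out of reach before that subject has had time to have an event. Leaving out subjects in follow-up has the opposite effect, because events are counted at once and event-free subjects only after 24 weeks.

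Table 6 avoids the question by treating outcomes as instantaneous. The figures given for the chance of stopping a toxic regimen, the chance of stopping an acceptable one, and the number of subjects enrolled may then not describe the rule the DSMB applies.

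**Working it through.** **Inputs from the plan.** Section 8.5: prior Beta(1, 4), criterion P(p > 0.20) ≥ 0.90, the Table 5 boundary and the Table 6 figures. Section 8.3: 25 subjects over 2.5 to 3 years, with a stage break after 15.

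**Assumptions.** The plan gives no TRSAE timing within the 24 weeks. Three cases are shown: all events in the first 4 weeks, uniform over 24 weeks, and all in the last 4 weeks. Entry is random at a constant rate. The boundary is checked at every event. The futility stop is left out, as it is in Table 6.

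**Step 1: Table 5.** With x events in n subjects the posterior is Beta(1 + x, 4 + n − x). The smallest x with upper tail at 0.20 of at least 0.90 matches the printed table for every n from 3 to 25. The exception is n = 2. Two events in two subjects give Beta(3, 4), and P(p > 0.20) equals the probability of at most 2 successes in 6 trials at 0.20: 0.8⁶ + 6(0.2)(0.8⁵) + 15(0.2²)(0.8⁴) = 0.2621 + 0.3932 + 0.2458 = 0.901. That meets the 90% criterion, but the table prints 3.

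**Step 2: Table 6 with instant outcomes.** Let a(n, x) be the probability of reaching n subjects with x events and no stop. Then a(n, x) = (1 − p)·a(n−1, x) + p·a(n−1, x−1), and any mass at or above the boundary is moved to stopped.

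| p | 0.10 | 0.15 | 0.20 | 0.25 | 0.30 | 0.35 | 0.40 | 0.45 |
|---|---|---|---|---|---|---|---|---|
| Stopped, recomputed (%) | 1.7 | 7.0 | 18.4 | 35.7 | 55.5 | 73.4 | 86.4 | 94.1 |
| Stopped, Table 6 (%) | 1.8 | 7 | 18.2 | 35.7 | 55.5 | 73.2 | 86.4 | 94.1 |
| Mean subjects, recomputed | 24.7 | 23.9 | 22.4 | 20.1 | 17.3 | 14.4 | 11.8 | 9.7 |
| Mean subjects, Table 6 | 24.7 | 23.9 | 22.4 | 20.1 | 17.3 | 14.5 | 11.8 | 9.7 |

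Table 6 is therefore correct for a rule in which each outcome is known before the next entry.

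**Step 3: overlap in practice.** 2.5 to 3 years is 130 to 156 weeks, or one entry every 5.2 to 6.2 weeks over 25 subjects. The number inside a 24-week window is then 24/6.2 to 24/5.2, about 4 to 5.

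**Step 4: denominator = all enrolled (the literal column label).** Calendar-time simulation with 20,000 runs per case, standard error at most √(0.25/20,000) = 0.35 points. With the event delay set to zero it returns 18.3%, 55.2% and 86.1% at p = 0.20, 0.30 and 0.40, so it agrees with Step 2. The ranges cover 2.5 and 3 years, with and without a pause after subject 15.

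| Event timing (assumed) | Stopped, p = 0.20 | Stopped, p = 0.30 | Stopped, p = 0.40 | Mean enrolled, p = 0.30 | Mean enrolled, p = 0.40 |
|---|---|---|---|---|---|
| Stated in Table 6 | 18.2% | 55.5% | 86.4% | 17.3 | 11.8 |
| First 4 weeks | 16.9–18.0% | 53.6–54.1% | 84.8–85.9% | 17.7–17.8 | 12.3–12.5 |
| Uniform | 11.7–13.4% | 45.0–48.0% | 80.5–82.0% | 19.6–20.3 | 14.8–15.7 |
| Last 4 weeks | 8.0–10.6% | 38.9–43.5% | 77.3–79.5% | 20.8–22.2 | 16.6–18.6 |

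Without a pause, the late-event figure at p = 0.30 is 38.9–41.3%. Other accrual conventions take the uniform figure at p = 0.30 down to about 43%.

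**Step 5: denominator = subjects with an event or 24 completed weeks.** At p = 0.20 (stated 18.2%), stopping is about 18–19% with late events, 24–29% with uniform events and 34–38% with early events. These figures move by a few points with the accrual convention. With uniform events and 2.75 years of accrual, stopping at p = 0.30 is 63.8% (stated 55.5%).

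**Step 6: strict enrolment order, each subject counted once an event or 24 weeks is reached and all earlier subjects are resolved.** The stopping row of Table 6 is recovered, because the sequence of outcomes is the same. The enrolment row is not: about 19 are enrolled on average at p = 0.30 (stated 17.3) and about 13 to 15 at p = 0.40 (stated 11.8).

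**The case against.** A reader might infer that the rule, as run, simply stops less often and later than stated. The documents do not support that. The denominator is undefined, and Step 5 shows that another ordinary reading stops more often. Even on the enrolled reading, the lower stopping rate at p = 0.20 is an advantage, since fewer acceptable regimens would be stopped.

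A reader might also take the sentence that includes all participants in safety monitoring as an instruction to count subjects in follow-up as event-free. Its natural meaning is that nobody is left out of the safety population. Only the column label points to the enrolled count.

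The size is also open to challenge. If TRSAEs come early, the enrolled reading costs only about 1 to 2 points at p = 0.30 and under one extra subject at p = 0.40. The large gaps need uniform or late events, and the plan supports neither.

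Finally, section 8.5 draws only a qualitative conclusion: stopping is unlikely below 20% and likely above it. At p = 0.40 the enrolled reading still stops in 77% of trials or more. The boundary is not the only safeguard. Section 9.1 lets the DSMB recommend early termination, and section 9.2.4.2 sends it unexpected related serious events within 7 or 15 days.

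These points limit the direction, the size and the consequence. They do not remove the core: the denominator is undefined, and Table 6 describes a rule that cannot be run in real time under the projected accrual.

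**Conclusion.** The point stands as a mismatch between the stated operating characteristics and any real-time use of the boundary. Neither real-time denominator reliably gives Table 6, and the two miss in different directions.

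- **All enrolled:** stopping at p = 0.30 is about 53–54% (early), 43–48% (uniform) or 39–41% (late; up to 43.5% with a pause), against 55.5%. Mean enrolment at p = 0.40 is about 12 to 19, against 11.8. Stopping at p = 0.20 falls to about 8–18%, against 18.2%.
- **Event or 24 weeks completed:** stopping at p = 0.20 is close to the stated value if events are late and rises to as much as about 38% if they are early.

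All of these figures rest on the assumed event timing, on 2.5 to 3 years of accrual and on continuous checking. If the boundary were checked only at the 6- to 12-month DSMB reviews in section 9.1, stopping would come later.

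The rule still works as a safeguard, so this should be corrected but does not invalidate the design. The n = 2 discrepancy is a separate, small inconsistency between Table 5 and its own criterion.

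**What to change.** 1. In section 8.5, define the Table 5 denominator and say how a subject with less than 24 weeks of follow-up and no event is counted.
2. Restate all rows of Table 6 (stopping probability, average subjects, average TRSAEs) from a simulation of that rule. Use staggered entry at the projected accrual and a stated range of event times. Say whether average subjects means enrolled or assessed.
3. If the boundary is to be applied in enrolment order to subjects with an event or 24 weeks of follow-up, the present stopping row can stay. The average number enrolled must still be restated. The section should also disclose that a known TRSAE would wait to be counted until all earlier subjects are resolved.
4. When Table 5 is re-issued, reconcile the entry for two events in two subjects with the 90% criterion.

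The cost is a short definition and a re-run simulation. No dose, visit or eligibility rule changes. The downside is that the restated stopping probabilities or the number of subjects exposed may look less favourable than those now printed.

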Eltrombopag is safe and relatively non-toxic with prolonged use. The EXTEND study (NCT00351468), an open label dose modification extension study evaluating the safety and efficacy of extended therapy of EPAG in ITP subjects, has been designed to assess long-term effects of EPAG therapy. At the most recent analysis of 302 patients (presented at EHA, 2016) the median average daily dose was 50.4 mg. The median duration of exposure to EPAG was 2.4 years (range, 2 days to 8.8 years). EPAG was well-tolerated, and both bleeding and clinically-significant bleeding decreased from baseline at all time points. AEs and SAEs occurred in 92% and 32% of patients respectively. SAEs considered possibly drug-related occurred in 8% of patients. AEs leading to withdrawal occurred in 14% of patients. The most frequent AEs leading to withdrawal were increased ALT (n=5), increased bilirubin (n=4), cataracts (n=4), and DVT (n=3). Nineteen patients (6%) reported thromboembolic events (TEEs), and 37 reported hepatobiliary laboratory abnormalities. ITP patients have return of their platelet counts to baseline within 1-2 weeks of discontinuation of drug.

In our cohort of 43 patients treated for refractory severe aplastic anemia (SAA), responses only began to be observed at the 3-month time point, and with continued exposure to drug, blood counts of all lineages improved towards the normal range gradually. Maximal response was not reached at 6 months with bone marrow cellularity normalizing by 9-15 months. Eighteen of 43 patients with refractory SAA had drug discontinued for robust response. Only 2 patients showed a decrease in counts clearly related to the discontinuation of EPAG. Re-initiation of EPAG restored hematopoiesis in both patients. However, EPAG was discontinued in one patient because of an intermittently detected cytogenetic abnormality. Since then the counts have remained stable and a repeat bone marrow biopsy showed a normal karyotype. These results suggest that the effect of EPAG on HSPC number or function is long-lasting and prolonged therapy may not be required in SAA.

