# 8.6. Off study criteria

*Per subject choice:* Subjects may withdraw from study at their request. The risks of withdrawing will be discussed, as will alternative treatment options. Those subjects who choose to withdraw while taking eltrombopag will be strongly encouraged to continue to have labs monitored until he/she initiates alternative therapy.

**Per principal investigator decision:** Should any of the following events occur during the study period, or in the extension treatment arm in responders, EPAG will be discontinued. The subject will be followed until resolution of the event. For study purposes labs relevant to the adverse event will be monitored for 30 days after discontinuation of EPAG. We will offer patients a follow-up evaluation at the NIH 6 months following being taken off EPAG treatment either due to lack of response or because they met other criteria for coming off study, but this visit will not be required. If they do not return to the NIH, we will contact their primary hematologist for information on their current hematologic status 6 months following their final dose of eltrombopag, and then take

them off study. If a patient initiates an alternative disease directed therapy at any time, the subject's participation on this study will be considered complete and the subject will go off study.

- Intolerance of EPAG not resolved by dose reduction
- Life threatening acute hypersensitivity reaction
- Thrombosis/embolism (DVT, PE, stroke or TIA, myocardial infarction) other than central line thrombosis
- Persistent hepatotoxicity as defined in §10.3.1
- New or worsening morphological abnormalities or cytopenia(s) indicative for transformation to MDS or AML
- No treatment response by week 24 (+/- 7 days)
- Any Grade IV toxicity considered related to the study medication excluding readily reversible metabolic or laboratory abnormalities or hematologic toxicities (see §9.2.1, 10.3.1)
- Significant progression of disease such as development of a solid tumor while on EPAG, or a concomitant condition that would make the subject ineligible for further protocol participation
- Pregnancy or unwillingness to use acceptable forms of contraception
- Initiation of non-protocol therapy for Diamond-Blackfan anemia
- Subject non-compliance
- Lost to follow-up

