9.2.2. Adverse events Management

AEs will be graded by severity utilizing CTCAE version 5.0 (summarized in Table 7) and attributed (unrelated, unlikely, possibly, probably or definitely) to study medication and/or disease (Table 8). The current CTCAE grading criteria can be downloaded from the CTEP homepage at:

https://ctep.cancer.gov/protocolDevelopment/electronic\_applications/ctc.htm.

Grade	Category	Description
1	Mild	Mild; asymptomatic; clinical or diagnostic observations only; intervention not indicated
2	Moderate	Moderate; minimal, local or noninvasive intervention indicated; limiting age-appropriate instrumental ADL 
3	Severe	Severe or medically significant but not immediately life-threatening; hospitalization or prolongation of hospitalization indicated; disabling; limiting self-care ADL 
4	Life threatening	Life-threatening consequences; urgent intervention indicated
5	Death	Death related to AE
1-		

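### The stopping rule in 8.5 gives a drug-related death the same weight as any related Grade IV event, and nothing in the plan pauses accrual after one

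*Combined protocol and SAP*

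**What the plan says.** Section 8.5 names the events that count, provided they are probably or definitely related to eltrombopag:

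- Item 1 covers fatal events: "Death considered to be probably or definitely related to eltrombopag".
- Item 2 covers life-threatening events of every kind, with one exclusion: "Any Grade IV toxicity excluding readily reversible metabolic or laboratory abnormalities".
- Item 3 then names one kind of event separately: "Grade IV thrombosis/embolism".

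The anticipated rate of the composite within 24 weeks is 20% or less. The prior is Beta(1, 4). The boundary is reached when the posterior probability that the true rate exceeds 20% is at least 90%. Table 5 gives the limits as a count of affected subjects, under the column heading "Stop if the number of subjects who have developed any of the specified TRSAE's reaches". The limits are 3 (n up to 5), 4 (to 9), 5 (to 12), 6 (to 16), 7 (to 20), 8 (to 24) and 9 (at 25). After giving the prior a weight of 5/25, the section adds: "Hence when we make decisions about stopping the study, the data from the study will dominate over the prior opinion".

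Section 9.2.3 again puts death and Grade IV toxicity together and has no separate provision for death.

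Outside the boundary:

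- Section 9.1 lets the DSMB recommend early termination and sets its review interval at 6 to 12 months.
- Section 9.2.4.2 sends it unexpected related fatal or life-threatening events within seven days.
- Sections 5.5.1 and 8.6 take a subject off drug for listed thromboses with no grade threshold. The 8.6 entry reads "Thrombosis/embolism (DVT, PE, stroke or TIA, myocardial infarction) other than central line thrombosis".

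**The concern.** A pooled safety count is a usual design, but a 20% benchmark that suits Grade IV toxicity is a very tolerant one for death. Because each affected subject adds one to the count whatever the event, the limit that lets the trial continue after two reversible but life-threatening toxicities also lets it continue after two drug-related deaths. The trial enrolls from age 2, and the protocol calls the drug's efficacy in this population unknown. If a related death occurs early, the plan should say what happens to the next subject waiting to enroll. At present it leaves that to reporting lines and DSMB discretion.

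The thrombosis item raises a related question. Section 8.5 singles thrombosis out, but the item as worded may add no event to the count.

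**Working it through.** **Inputs (all from 8.5):** prior Beta(1, 4); benchmark 0.20; threshold 0.90; the Table 5 limits; 25 subjects.

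**Formula.** With s affected subjects among n, the posterior is Beta(1+s, 4+n−s). For these integer parameters, P(rate > 0.20) = P(Binomial(n+4, 0.20) ≤ s).

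**Step 1: reproduce the plan.** The smallest s with posterior at least 0.90 equals the Table 5 limit at every n from 3 to 25. An exact recursion over 25 subjects, checking Table 5 after each, gives these percentages of trials stopped:

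| True rate | 0.10 | 0.15 | 0.20 | 0.25 | 0.30 | 0.35 | 0.40 | 0.45 |
|---|---|---|---|---|---|---|---|---|
| Table 6 | 1.8 | 7 | 18.2 | 35.7 | 55.5 | 73.2 | 86.4 | 94.1 |
| Exact | 1.7 | 7.0 | 18.4 | 35.7 | 55.5 | 73.3 | 86.4 | 94.1 |

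All agree within 0.2 points, so the boundary is sound for the composite it describes.

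**Step 2: deaths only.** Suppose every counted event is a related death.

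| Deaths / subjects | Posterior for rate > 0.20 | Table 5 limit | Stops? |
|---|---|---|---|
| 2 / 3 | 0.852 | 3 | no |
| 2 / 4 | 0.797 | 3 | no |
| 2 / 5 | 0.738 | 3 | no |
| 3 / 5 | 0.914 | 3 | yes |
| 3 / 9 | 0.747 | 4 | no |
| 4 / 9 | 0.901 | 4 | yes |

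For 2 of 5: 0.8⁹ + 9(0.2)(0.8⁸) + 36(0.04)(0.8⁷) = 0.134 + 0.302 + 0.302 = 0.738.

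**Step 3: how often Table 5 would stop on deaths alone.** The related-death rates below are assumptions; the protocol gives none.

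| Assumed rate | 1% | 2% | 5% | 10% |
|---|---|---|---|---|
| Trials stopped | 0.001% | 0.009% | 0.17% | 1.7% |

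At 5%, two or more deaths among five subjects has probability 2.3%; at 2% it is 0.4%. Such a result would be surprising even at those rates, yet Table 5 does not react to it.

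**Step 4: the thrombosis item.** Grade IV thrombosis is a Grade IV toxicity and is not a readily reversible metabolic or laboratory abnormality. Item 3 therefore lies wholly inside item 2 and adds no event. Table 7 describes Grade 3 as "Severe or medically significant but not immediately life-threatening; hospitalization or prolongation of hospitalization indicated", so a thrombosis at that level is not counted in 8.5, although 5.5.1 and 8.6 act on listed thromboses of any grade. The exemption for central-line thrombosis appears in 8.6 but not in 5.5.1.

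**Step 5: table against criterion at n = 2.** For 2 of 2: 0.8⁶ + 6(0.2)(0.8⁵) + 15(0.04)(0.8⁴) = 0.262 + 0.393 + 0.246 = 0.901. This meets the 90% criterion, but Table 5 asks for 3, which two subjects cannot reach. Table 6 was evidently run on Table 5 as printed: stopping at 2 of 2 would give 2.4% at a rate of 0.10 and 19.8% at 0.20.

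**Step 6: prior weight.** The prior is worth 5 subjects. Against the data that is 5/25 = 20% at n = 25, but 5/5 at n = 5, where prior and data weigh the same. Below n = 5 the prior weighs more.

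**The case against.** The best defence is that 8.5 never claims to be a death rule. It defines a composite, gives that composite its own benchmark, and calibrates the boundary correctly. Deaths are handled elsewhere. The DSMB can recommend termination without any boundary being crossed. Death is not on the expected-event lists in 10.3.1, so a related death should qualify for the seven-day report. The drug supplier receives every SAE within 24 hours. Accrual is slow: 25 subjects over 2.5 to 3 years is 30/25 to 36/25, or about 1.2 to 1.4 months per subject, so few would enroll while a report is read. Two deaths also use up two of the three counts, so one more affected subject by n = 5 reaches the limit.

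Most of this stands, and it limits how serious the gap is. It does not close it. Reporting is not a pause, and DSMB review is otherwise scheduled every 6 to 12 months.

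A reader might infer more than the documents support:

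- *That thrombosis short of Grade IV or beyond it can never trigger the rule.* A related fatal thrombosis is Grade 5 and counts under item 1. Only Grades I to III go uncounted.
- *That two early deaths can never meet the plan's criterion.* At 2 of 2 the written criterion is met; it is Table 5 that does not stop.
- *That the trial would run on through eight deaths.* Table 5 alone permits eight at n = 25, but that would require the DSMB to stay silent throughout.
- *That uncounted thromboses are likely to be numerous.* Section 2.4.6 reports "Nineteen patients (6%) reported thromboembolic events (TEEs"), but in ITP, over a median exposure of 2.4 years and without attribution. Section 2.4.3 says ITP carries a raised thrombotic risk of its own, and 4.2.18 excludes most prior thromboembolism. No 24-week rate for this population can be read from it.

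**Conclusion.** The main point holds as a gap in the formal rule, not as an error in its calculation. Table 5 follows from the stated prior, benchmark and threshold at every n from 3 upward, but it is nearly unresponsive to drug-related deaths: it continues at 2 of 5 and 3 of 9, and stops about 0.2% of trials on deaths alone at an assumed 5% rate and 1.7% at 10%. The continue/stop findings need no outside figure; the percentages depend on the assumed rates. Because DSMB discretion and the seven-day report exist, this is an inexpensive improvement to make and not evidence that subjects are unprotected.

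Three secondary points also hold. Item 3 is redundant, and 8.5, 5.5.1 and 8.6 are not aligned on thrombosis. Table 5 and the written criterion disagree at n = 2. The sentence on data dominating the prior is true at n = 25 but not at or below n = 5; correcting it changes no boundary.

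**What to change.** **Main change.** Add to 8.5 that any death probably or definitely related to eltrombopag suspends new accrual until the DSMB has reviewed it, and repeat this in the DSMB text of 9.1 or 9.2.4.2. Keep Table 5 for the pooled composite. The cost is a sentence or two and a possible short pause in a trial expected to accrue over 2.5 to 3 years. Tables 5 and 6 are unaffected.

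**Secondary changes.**

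- *Thrombosis.* Reconcile 8.5, 5.5.1 and 8.6, including the central-line exemption. Then either delete item 3 or state which thromboses count at study level. If the set is widened, confirm that the 20% benchmark and the Beta(1, 4) prior still apply, since both were set for the current list. State the attribution requirement too: 8.5 requires probable or definite relation, while the thrombosis entries in 5.5.1 and 8.6 require none. As an illustration on assumed rates, adding 6% lower-grade thrombosis to 5% currently counted events moves the rate from 0.05 to 0.11, and stopping from 0.2% to 2.4%.
- *Two subjects.* Either change Table 5 at n = 2 or state that monitoring starts at n = 3.
- *Prior weight.* Say that the prior carries 20% of the weight of the data at n = 25 and equal weight at n = 5.
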